13.6.2 FreeLite™ Disease Response Criteria

Table 18

Response	FreeLite™ criteria
CR	For those patients being followed by serum free light chain (and NO measurable serum or urine M-spike), which were immunofixation negative at enrollment, normalization of serum free light chain ratio. Normalization is defined as the serum free light chain ratio being within the normal range. If the serum free light chain ratio is not within the normal range, but the individual kappa and lambda light chain values are within normal range, this may be considered CR.
PR	If only measurable parameter is serum immunoglobulins free light chain (FLC), EITHER of the following changes qualify as partial response: 
 - A 50% decrease in the difference between involved and uninvolved FLC levels; OR - A 50% decrease in the level of involved FLC AND a 50% decrease (or normalization) in the ratio of involved/uninvolved FLC
Progressive Disease	If only measurable parameter is serum immunoglobulins free light (FLC), either of the following qualify as progression: 
 - 50% increase in the difference between involved and uninvolved FLC levels from the lowest response level, which must also be an absolute increase of at least 10 mg/dL; OR - 50% increase in the level of involved FLC AND a 50% increase in the ratio of involved/uninvolved FLC from the lowest response level.

14. Statistical Considerations

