13.4. Measurement of Effect

Patients enrolled onto this trial must have measurable disease defined as disease that can be measured either by serum or urinary evaluation of the monoclonal component or by serum assay of FLC and is defined by at least one of the following three measurements:

- Serum M-protein > (0.5 g/dl) g/dl
- Urine M-protein > 200 mg/24 h
- Serum FLC assay: Involved FLC level > 10 mg/dl (> 100 mg/l) provided serum FLC ratio is abnormal.

The disease response will be assessed using criteria based on the International Working Group Uniform Response Criteria in Section 15.3.1. If the only measurable parameter is serum immunoglobulins free light chain (FLC), the participant will be followed by FreeLite™ Disease Response Criteria provided in Section 15.3.2.

The same method of assessment and technique should be used for disease measurement

throughout the study. Disease response should be confirmed by two consecutive assessments at a minimum of 6 weeks apart.

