13.6. Response Criteria

13.6.1 International Myeloma Working Group Response Criteria

Table 17

Response	IMWG criteria
sCR	CR as defined below plus normal FLC ratio and absence of clonal cells in bone marrow by immunohistochemistry or 2 – 4 color flow cytometry
CR	Negative immunofixation on the serum and urine and disappearance of any soft tissue plasmacytomas and < 5% plasma cells in bone marrow. In patients with only FLC disease, a normal FLC ratio of 0.26–1.65 is required.
VGPR	Serum and urine M-protein detectable by immunofixation but not on electrophoresis or ≥ 90% reduction in serum M-protein plus urine M-protein level < 100 mg/24 h In patients with only FLC disease, >90% decrease in the difference between involved and uninvolved FLC levels is required.
PR	≥ 50% reduction of serum M-protein and reduction in 24 hours urinary M-protein by ≥90% or to < 200 mg/24 h If the serum and urine M-protein are unmeasurable, a ≥ 50% decrease in the difference between involved and uninvolved FLC levels is required in place of the M-protein criteria
Stable disease	Not meeting criteria for CR, VGPR, PR, or progressive disease

Progressive disease	
Increase of $\geq 25\%$ from lowest response value in any one or more of the following:
 
Serum M-component and/or (the absolute increase must be $\geq 0.5 \text{ g/dL}$) Urine M-component and/or (the absolute increase must be $\geq 200 \text{ mg/24 h}$) Only in patients without measurable serum and urine M-protein levels; the difference between involved and uninvolved FLC levels. The absolute increase must be $> 10 \text{ mg/dL}$
 
Definite development of new bone lesions or soft tissue plasmacytomas or definite increase in the size of existing bone lesions or soft tissue plasmacytomas Development of hypercalcaemia (corrected serum calcium $> 11.5 \text{ mg/dL}$ or 2.65 mmol/L) that can be attributed solely to the plasma cell proliferative disorder

---------------------	--

Additional response criteria for specific disease states

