14.3.2 Statement for Primary Endpoint

The primary endpoint of the dose escalation portion of this phase I study is the MTD. The maximum tolerated dose is defined as the highest dose level among those tested where at most one out of 6 patients develops a DLT prior to the start of their second cycle of treatment and the next highest dose level is such that 2 or more patients among the maximum of 6 patients treated at that dose level developed a DLT prior to the start of their second cycle of treatment.

The primary endpoint of the expansion portion of this phase I study is the objective response rate. The objective response rate is the percent of patients who meet the International Myeloma Working Group Response Criteria for sCR, CR, VGPR, or PR on two consecutive evaluations at least 4 weeks apart among the patients who began study treatment. A 90% binomial confidence interval will be constructed for the overall objective response rate.

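### Patients measurable only by free light chain are followed by Table 18 but counted by Table 17, and the two complete-response rows conflict

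*Combined protocol and SAP*

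**What the plan says.** Section 13.4 sets the route for these patients: "If the only measurable parameter is serum immunoglobulins free light chain (FLC), the participant will be followed by" the FreeLite criteria, which are Table 18 in Section 13.6.2. Its cross-references (15.3.1 and 15.3.2) do not lead to response criteria; Section 15.3 is Informed Consent.

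Table 18, CR row, covers FLC-followed patients "which were immunofixation negative at enrollment". It asks for "normalization of serum free light chain ratio. Normalization is defined as the serum free light chain ratio being within the normal range". If the ratio is abnormal, "but the individual kappa and lambda light chain values are within normal range, this may be considered CR". The row states no plasma-cell limit, no plasmacytoma condition and no minimum fall in FLC.

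Table 17 (Section 13.6.1), CR row, requires negative serum and urine immunofixation, "disappearance of any soft tissue plasmacytomas and < 5% plasma cells in bone marrow", and adds: "In patients with only FLC disease, a normal FLC ratio of 0.26–1.65 is required". For PR when M-protein is unmeasurable, a "50% decrease in the difference between involved and uninvolved FLC levels is required in place of the M-protein criteria".

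Section 14.3.2 names the objective response rate (ORR) as the primary endpoint of the expansion and defines it as "the percent of patients who meet the International Myeloma Working Group Response Criteria for sCR, CR, VGPR, or PR", confirmed on two consecutive evaluations, with a 90% binomial interval. It does not mention Table 18.

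Section 13.5 says marrow aspiration and biopsy will be done to confirm CR. It gives no plasma-cell limit. Table 15 lists marrow only at screening and at the end of cycle 1.

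**The concern.** The same patient falls under two rules, and no text says which one decides the response that enters the ORR. The rules differ in substance: Table 18 can award its top category to a patient whose FLC change is too small for PR. A site that follows 13.4 as written may record a response that the definition in 14.3.2 would not accept. The expansion has 4, 7 or 10 patients, so one classification is visible in the estimate. The trial is open label, so if the table is chosen after the data are in, the results could influence the rule.

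**Working it through.** The plan gives no response-rate or sample-size figure that rests on Table 18, so there is none to reproduce. The check is whether a patient can meet Table 18 CR and fail PR, and for which baseline ratios.

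**Inputs.**
- FLC entry criterion (3.1): involved chain at least 10 mg/dL and an abnormal ratio.
- Normal kappa/lambda ratio (Table 17): 0.26 to 1.65.
- PR: at least a 50% fall in involved minus uninvolved FLC (both tables), or in Table 18 a 50% fall in the involved chain together with a 50% fall in, or normalization of, the ratio.

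**Example 1.** An FLC-only patient, immunofixation negative at enrollment, goes from lambda 20, kappa 4 mg/dL to lambda 15, kappa 4.
- Ratio: 4/20 = 0.200 (abnormal) to 4/15 = 0.267 (normal).
- Involved chain: 1 − 15/20 = 25% fall.
- Difference: 16 to 11, a fall of 5/16 = 31%.
- PR fails in both tables. Table 18 CR is met.

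**Example 2.** Lambda 10, kappa 2.5 mg/dL goes to lambda 10.5, kappa 2.8.
- Ratio: 0.250 to 0.267.
- The involved chain rises 5%. The difference rises from 7.5 to 7.7 (2.7%).
- The FLC part of Table 18 CR is still met.

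**Range affected.** Let R0 be the baseline involved/uninvolved ratio and L the normal limit on that scale: 1.65 for kappa, 1/0.26 = 3.85 for lambda. With the uninvolved chain constant and the ratio just reaching L:
- fall in the difference = 1 − (L − 1)/(R0 − 1), which is under 50% when R0 < 2L − 1;
- kappa: 1.65 < R0 < 2.30; lambda: 3.85 < R0 < 6.69;
- at the top of each band the involved chain has fallen 1 − L/R0 = 28% (kappa) or 43% (lambda), so the second PR route in Table 18 also fails.

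If the uninvolved chain doubles, the upper limits rise to 1 + 4(L − 1) = 3.60 and 12.4. At a baseline ratio of 30, normalization implies a 98% (kappa) or 90% (lambda) fall in the difference, and the anomaly disappears.

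**Class under Table 17.** Example 1 fails PR and has a normal ratio. It is CR if immunofixation is negative, plasma cells are under 5% and there is no plasmacytoma. Otherwise it is stable disease, a non-responder.

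**Reverse case.** Take the FLC values of example 1 in a patient who was immunofixation positive at entry with no measurable M-protein, and who becomes negative with under 5% plasma cells and no plasmacytoma. Table 17 gives CR. The Table 18 CR row does not cover this patient, and PR fails.

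**Effect of one patient on ORR (exact 90% intervals).**

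| Cohort | Without | With | Shift |
|---|---|---|---|
| 10 | 3/10 = 30% (8.7 to 60.7) | 4/10 = 40% (15.0 to 69.6) | 10 points |
| 7 | 1/7 = 14.3% (0.7 to 52.1) | 2/7 = 28.6% (5.3 to 65.9) | 14.3 points |
| 4 | 1/4 = 25% (1.3 to 75.1) | 2/4 = 50% (9.8 to 90.2) | 25 points |

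The starting counts are illustrative.

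**The case against.** - **Table 17 CR has no minimum FLC fall either.** A reader might infer that reaching CR while failing PR is peculiar to Table 18. It is not: example 1 with clean marrow, negative immunofixation and no plasmacytoma is CR in both tables. This stands. The conflict lies in the marrow, immunofixation and plasmacytoma conditions and in the abnormal-ratio sentence.
- **Marrow is already called for.** Section 13.5 has no FLC-only exception, and Table 15 footnote e allows CT to confirm CR where clinically indicated. So it would be wrong to say that the plan has no marrow check. But 13.5 sets no threshold, and Table 18 gives none to confirm against.
- **Read literally, 14.3.2 admits only IMWG responses**, so a response met only in Table 18 would stay out of the ORR. A reader might infer a demonstrated upward bias. The documents show an unresolved conflict, not a bias that must occur, and the reverse case shows that it can also lose responders.
- **The abnormal-ratio sentence may not change the ORR.** At entry the difference exceeds 10 − 10/1.65 = 3.94 mg/dL (kappa) or 10 − 2.6 = 7.4 mg/dL (lambda). The plan gives no normal limits for the individual chains. If the upper limits are assumed to be at most 1.97 and 3.7 mg/dL, two normal chains imply at least a 50% fall, so PR is already met and the sentence only relabels PR as CR. It still contradicts Table 17.
- **The affected group is narrow.** With the uninvolved chain constant, the bands need uninvolved FLC of at least 10/2.30 = 4.35 (kappa disease) or 10/6.69 = 1.49 mg/dL (lambda disease), and the response must be confirmed. The ORR has no decision rule, and Section 2.4.1 lists it as secondary. This limits the size of the problem but does not remove the contradiction.

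**Conclusion.** The contradiction is real. Section 13.4 routes FLC-only patients to a table whose CR row conflicts with the one that 14.3.2 uses to count responses. Among those immunofixation negative at enrollment, a patient with a baseline ratio near normal can be CR by Table 18, fail PR in both tables, and be a non-responder by Table 17 when its marrow, immunofixation or plasmacytoma condition is not met. The bands of 1.65 to 2.30 (kappa) and 3.85 to 6.69 (lambda) assume a constant uninvolved chain.

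The mismatch mainly adds responders and can occasionally remove one. The per-patient shifts of 10 to 25 points assume that the ORR is read on the expansion patients alone; on all 19 to 25 patients, one patient is 1/19 = 5.3 to 1/25 = 4.0 points. The number of FLC-only patients is not stated. From 0 to 3 of 10 is an assumption, and those inside the bands would be fewer. The total effect is therefore probably small, but it cannot be bounded from the documents.

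**What to change.** 1. In 13.4 and 14.3.2, state that FLC-only patients are classified for the ORR by the FLC provisions of Table 17, and correct the cross-references in 13.4.
2. Align the Table 18 CR row with Table 17 CR: ratio within 0.26 to 1.65, negative immunofixation at response, under 5% plasma cells on the marrow already called for in 13.5, and no plasmacytoma. Negative immunofixation at response then replaces the enrollment condition, which also resolves the reverse case.
3. Delete the sentence that allows CR with an abnormal ratio.

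Do not add a minimum FLC fall to Table 17 CR. Nothing in the documents supports it, and it would reclassify patients who meet every condition there.

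The cost is wording in three sections and no new test. The ORR or CR rate may come out slightly less favourable, and an FLC-only patient without a confirmatory marrow is not classed as CR. The change should be made before responses are classified.

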2.4. Endpoints

2.4.1 Primary and Secondary

Primary:

1. Maximum tolerated dose (MTD): The maximum tolerated dose (MTD) is defined as the highest dose level among those under consideration where at most 1 of 6 patients develops a dose limiting toxicity and 2 or more of the 3-6 patients treated at the next higher dose level develop a dose limiting toxicity.
2. Safety profile: The maximum grade of each type of toxicity will be recorded for each patient. For each toxicity reported by dose level, the percentage of patients developing any degree of that toxicity as well as the percentage of patients developing a severe degree (Grade 3 or higher) due to treatment will be determined.

Secondary:

1. Progression free survival (PFS) defined as the time from study entry to the documentation of disease progression using IMWG criteria or death due to any cause.
2. Overall survival (OS) is defined as time from registration to death due to any cause.
3. Overall Response rate(ORR)
4. Duration of response, defined as the time from documented response to disease progression among those patients whose disease meets the IMWG criteria for disease response.
5. Safety Profile: CTCAE v5.0 will be used to grade and assign attribution to each adverse event reported.

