8.3. Criteria for Discontinuation of Protocol treatment

Patients are continued on treatment until any of the criteria for discontinuation of protocol therapy is met, which includes:

- Tumor progression
- Request by the patient to withdraw
- Unacceptable adverse events
- Treatment delay of >4weeks
- Intercurrent illness which would, in the judgment of the investigator, affect assessments of clinical status to a significant degree or require discontinuation of drug

Administration of non-protocol anti-tumor drug during the trial. Patients who discontinue treatment for any of the above reasons will go to survival follow-up where late toxicities and clinical outcome information will be collected every 6 months for a maximum of 2 years post registration. Once a patient has entered the survival follow-up phase of the trial, his/her therapy is at the discretion of the treating physician.

9. Study Assessments and Procedures

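### For FLC-only patients, Table 18's second progression route has no minimum rise, can be met while the ratio test for complete response still holds, and can disagree with the IMWG rule named for PFS

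*Combined protocol and SAP*

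**What the plan says.** Section 13.4 routes FLC-only patients to the FreeLite criteria: "If the only measurable parameter is serum immunoglobulins free light chain (FLC), the participant will be followed by" those criteria. (It cites a Section 15.3.2; the criteria are in 13.6.2, Table 18.)

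Table 18 offers two routes to progression, either of which suffices:

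- Limb 1: a 50% rise in the difference between involved and uninvolved FLC, "which must also be an absolute increase of at least 10 mg/dL".
- Limb 2: "50% increase in the level of involved FLC AND a 50% increase in the ratio of involved/uninvolved FLC from the lowest response level". No absolute amount is attached.

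For complete response (CR), Table 18 asks patients who were immunofixation-negative at enrollment for a normal ratio: "Normalization is defined as the serum free light chain ratio being within the normal range". The range is in Table 17: "In patients with only FLC disease, a normal FLC ratio of 0.26–1.65 is required".

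Table 17, the IMWG table in Section 13.6.1, has its own progression rule for these patients. It requires a rise of at least 25% from the lowest value and more than 10 mg/dL, applied as follows: "Only in patients without measurable serum and urine M-protein levels; the difference between involved and uninvolved FLC levels". Section 2.4.1 defines the PFS event as "documentation of disease progression using IMWG criteria or death due to any cause".

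Section 8.3 makes progression a reason to stop: "Patients are continued on treatment until any of the criteria for discontinuation of protocol therapy is met". Section 14.3 counts progression as an event for duration of response and for PFS, and lists PFS for the expansion cohort.

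**The concern.** A minimum on one of two alternative routes protects little if the other route can be met below it. At low nadirs, where responders sit, a 50% relative rise can be a very small absolute one. The same FLC values may then count as progression while still passing the ratio test for CR, and no rule says which category prevails.

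Separately, two sections point the same patients to different progression rules. The call and its date, and with them the end of protocol treatment, would depend on which section a site or analyst follows.

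**Working it through.** The plan gives no figure to reproduce. The rules come from Tables 17 and 18. The FLC values below are illustrative, in mg/dL, because the documents give no patient values. Write I for involved FLC, U for uninvolved, r = I/U and D = I - U.

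**1. When limb 2 falls below the minimum.** With U unchanged, a 50% rise in I raises r by 50% and D by 0.5 x I. This is under 10 when I < 20. Limb 2 is met on a rise of 0.4, 2.75, 5 and 7.5 at involved nadirs of 0.8, 5.5, 10 and 15.

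**2. What limb 2 adds to limb 1.** D = I(1 - 1/r). If both nadirs come from one visit with r > 1, then D'/D = (I'/I) x (1 - 1/r')/(1 - 1/r). The first factor is at least 1.5, and the second exceeds 1 because r' > r. Meeting limb 2 therefore means D is up at least 50%. If D is also up 10 or more, limb 1 is already met, so limb 2 adds only calls below the minimum.

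This fails when the nadirs come from different visits. Take I/U of 60/15, then 120/60, then 90/30: r is 4, 2, 3 and D is 45, 60, 60. At the third visit I is 90/60 = 1.5 times its lowest value and r is 3/2 = 1.5 times its lowest, so limb 2 is met. D is up 15, or 15/45 = 33%, so limb 1 is not met. Here limb 2 adds a call above the minimum.

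**3. Worked cases.**

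| I/U, nadir to visit | I | r | D | Limb 1 | Limb 2 | Table 17 |
|---|---|---|---|---|---|---|
| 0.8/0.8 to 1.2/0.8 | +50% | 1.0 to 1.5 (+50%) | 0 to 0.4 | no | yes | no |
| 10/1 to 15/1 | +50% | 10 to 15 (+50%) | 9 to 14 (+5, +55.6%) | no | yes | no |
| 32/2 to 44/2 | +37.5% | 16 to 22 (+37.5%) | 30 to 42 (+12, +40%) | no | no | yes |

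Row 1 also passes the CR ratio test. Reading the normal range as kappa/lambda, the ratio is 1.5 if kappa is involved and 1/1.5 = 0.67 if lambda is; both lie within 0.26-1.65. Overlap with limb 2 is possible when the nadir I/U is at most 1.65/1.5 = 1.10 (kappa) or (1/0.26)/1.5 = 2.56 (lambda). Rows 2 and 3 show the two tables disagreeing in opposite directions.

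**4. Delay if a 10 mg/dL minimum is imposed.** With U unchanged, the delay in doublings of I is log2((I + 10)/(1.5 x I)):

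- I = 0.8: log2(10.8/1.2) = 3.2
- I = 5.5: log2(15.5/8.25) = 0.9
- I = 10: log2(20/15) = 0.4
- I = 15: log2(25/22.5) = 0.15
- I = 20: log2(30/30) = 0

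**5. Patients exposed.** The FLC-only share is not in the documents; 10-30% is assumed. Response anchors are in Section 1.1.2.1: single-agent lenalidomide (26% response, 2% CR) at the low end, and the Table 1 combination arms (up to 61% response, 15.9% CR) at the high end.

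| | All enrolled (19-25) | Expansion (4-10) |
|---|---|---|
| FLC-only | 19 x 0.10 = 1.9 to 25 x 0.30 = 7.5 | 4 x 0.10 = 0.4 to 10 x 0.30 = 3 |
| Responders | 1.9 x 0.26 = 0.5 to 7.5 x 0.61 = 4.6 | 0.4 x 0.26 = 0.1 to 3 x 0.61 = 1.8 |
| In CR | 1.9 x 0.02 = 0.04 to 7.5 x 0.159 = 1.2 | 0.4 x 0.02 = 0.01 to 3 x 0.159 = 0.5 |

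**The case against.** **Limb 2 may be deliberate.** It needs two concurrent 50% rises, mirrors the second partial-response route in Table 18 (also without a minimum), and may detect low-burden relapse sooner. This stands in part: nothing in the documents shows that a given limb 2 call would be wrong. But the plan sets a minimum of about 10 mg/dL in limb 1 and in Table 17, and does not say why limb 2 should do without one.

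**Section 13.4 is the specific rule and should govern.** That is a reasonable reading, and it would settle which table a site uses. It leaves PFS at odds with its definition in 2.4.1, and leaves the gap within Table 18.

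**A normal ratio at one visit is not a confirmed CR.** This is correct. Section 13.4 requires two consecutive assessments at least 6 weeks apart, and 13.5 adds bone marrow examination to confirm CR. A reader might infer from the first worked case that a patient is in established CR and in progression at once. The case shows only that the ratio criterion and limb 2 are both met. The confirmation sentence might also be stretched to cover progression, since Table 18's title spans every category, but it speaks of response and the plan states no confirmation for progression.

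**Limb 2 might look as though it does nothing except evade the minimum.** A reader might infer this from the algebra. Table 18 does not say that both nadirs come from one visit, and the 60/15, 120/60, 90/30 sequence is a counterexample. For the same reason, deleting limb 2 and adding 10 mg/dL to it are not equivalent unless nadirs are tied to one visit.

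**Conclusion.** The point holds as a minor defect of definition. Read literally, Table 18 can call progression on a rise well below the minimum in limb 1 and in Table 17, and can do so while its own CR ratio test is met. Sections 2.4.1 and 13.4 name different rules for the same patients, and those rules can disagree either way.

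The reach is small: PFS in the 4-10 patient expansion cohort, duration of response at all dose levels, and the decision to stop treatment in an individual patient. PFS and duration of response are estimated by Kaplan-Meier without a test. The MTD rests on first-cycle toxicity and is unaffected; ORR rests on the response categories and is essentially unaffected. The patient counts depend on the assumed 10-30% FLC-only share.

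A reader might go further and infer that a material share of progression dates would be wrong. The documents give neither FLC variability nor patient values, so they support no error rate, and none is claimed.

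**What to change.** Name one progression rule for FLC-only patients, in the same words, in Sections 2.4.1, 13.4 and 13.6. The simplest choice is Table 17's FLC-only rule, because 2.4.1 already names IMWG.

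If Table 18 is kept for progression:

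- require a rise of at least 10 mg/dL in the FLC difference for limb 2 as well;
- state that the nadirs of involved FLC and of the ratio are taken from the same visit;
- where the nadir difference is zero or below, so that a percentage rise has no meaning, use the 10 mg/dL alone;
- align the PFS definition in 2.4.1 with Table 18.

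The cost is wording, plus a re-check of any FLC-only progression calls already made, since Section 7.3 shows patients on dose level 2 by October 2021. No new measurement is needed: FLC is already taken on day 1 of each cycle (Table 15, footnote i). The clinical price is later dating of some true low-burden relapses, by about 3 doublings of involved FLC at a very low nadir and under one from 5.5 mg/dL upward. If earlier detection was the purpose of limb 2, the plan should say so and state which category prevails when the CR ratio test is also met.
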